#### **Gray Matter**

- (a) Caudate Left Hemisphere(mm3)
- (b) Caudate Right Hemisphere(mm3)
- (c) Frontal Lobe Left MCT (mm)
- (d) Frontal Lobe Left Vol (mm3)
- (e) Frontal Lobe Right MCT(mm)
- (f) Frontal Lobe Right Vol (mm3)
- (g) Globus Pallidus Left Hemisphere(mm3)
- (h) Globus Pallidus Right Hemisphere(mm3)
- (i) Putamen Left Hemisphere(mm3)
- (i) Putamen Right Hemisphere(mm3)
- (k) Thalamus Left Hemisphere(mm3)
- (1) Thalamus Right Hemisphere(mm3)

#### **White Matter**

- (a) Genu of Corpus FAR
- (b) Genu of Corpus ADR
- (c) Genu of Corpus MDR
- (d) Genu of Corpus RDR
- (e) Genu of Corpus FAL
- (f) Genu of Corpus ADL(g) Genu of Corpus MDL
- (h) Genu of Corpus RDL
- (i) Body of Corpus FAR
- (i) Body of Corpus ADR
- (k) Body of Corpus MDR
- (1) Body of Corpus RDR

- (m)Body of Corpus FAL
- (n) Body of Corpus ADL
- (o) Body of Corpus MDL
- (p) Body of Corpus RDL
- (q) Splenium FAR
- (r) Splenium ADR
- (s) Splenium MDR
- (t) Splenium RDR
- (u) Splenium FAL
- (v) Splenium ADL
- (w) Splenium MDL
- (x) Splenium RDL

#### 4.2. Safety Endpoints

#### 4.2.1. Exposure Duration and Summary of Dosing

Exposure duration will include durations between each treatment cycle and between first and last treatment cycles.

Dosing includes number of infusions and volumes infused in each visit.

#### 4.2.2. Adverse Events

Adverse events are as defined in the protocol Section 9.1. Additional details on Serious Adverse Events (SAEs), classification of AEs according to expectation (unexpected, expected), Severity (Mild, Moderate, Severe,) and causality (Certain, Probable/Likely, Possible, Unlikely and Conditional/Unclassified) are defined in sections 9.1.1, 9.1.2, 9.1.3 and 9.1.4 respectively in the protocol.

Treatment Emergent Adverse Events (TEAEs) are all Adverse Events that started on or after the first administration of study drug.

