7.2.4. Cardiogram

For the monitoring of cardiac function, an electrocardiogram (ECG) of 12 leads will be performed. The interpretation of the tracing should be performed by a physician and recorded both in the source document and in the individual clinical form (CRF) of each participant. Clinically significant abnormalities (and/or those related to current health condition) should be recorded as relevant medical history and/or current conditions during the Inclusion Visit (V-3), which should be judged by the Investigator Physician as a risk or not to inclusion in the study. Other clinically significant abnormalities found after product administration (compared to visit V-3) should be reported and evaluated by the Investigator physician as an adverse event. All ECG reports should be kept as part of the study documentation.

The electrocardiogram will be performed during visit V-3, in the scheduled post-cycle visits (V3, V7 and V11), and on the days when there is administration of the investigational product, the evaluation will be carried out during the 6 hours of hospitalization after the end of the administration (before the dismissal of the participant).

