8.5. Measurement of the Safety Variable

During the study, the safety of the investigational product will be thoroughly assessed based on periodic evaluations including clinical, laboratory and imaging tests, so that any alteration is properly recorded. The safety data described below will be collected and recorded in the clinical file:

- Adverse events: all adverse events will be monitored and reported in the clinical form of the study from the signature of the Informed Consent, including type, frequency, intensity, seriousness, severity, action taken and relationship with the investigational product of the study. The adverse events may be reported by the research participant or observed by the Researcher. Adverse events will be standardized by the Investigator.
- Changes in vital signs, clinical examination and medical evaluations;
- Changes in laboratory or serology tests:
- Change in electrocardiogram (ECG);
- Incidences and classification of benign and malignant neoplasms.

The results obtained will be presented through the proportion of adverse events that occur, segmented by dose of the investigational product. Any clinically significant abnormalities that persist until the end of the study will be monitored by the Principal Investigator until resolution or until a clinically stable outcome.

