9. ADVERSE EVENTS

9.1. Adverse events

An adverse event is defined as any unfavorable medical occurrence, which may occur during treatment with an investigational drug/product, but which does not necessarily have a causal relationship with this treatment.

All adverse events observed or reported spontaneously, regardless of the possible causal relationship with the investigational drug/product of the study, should be recorded on the Adverse Events page(s) of the clinical study form. Serious adverse events of any nature or unexpected events should be notified to Sponsor via specific Pharmacovigilance form.

Alterations (abnormalities) in the physical examination, considered as clinically significant by the Investigator, prior to the use of the investigational product should be reported in physical and/or historical clinical evaluation (if applicable) and if, after use of the drug, relative worsening, worsening of conditions or appearance of changes (abnormalities) during regular visits, these should be recorded as adverse events.

Changes (abnormalities) in the laboratory testing, considered as clinically significant by the Investigator and present in the period in which the participant does not use the medicine/ investigational product should also be recorded as adverse events. All laboratory alterations (abnormalities) should always be recorded in the participant's medical records.

For all adverse events, the Investigator should seek appropriate information, both to determine the consequence of the adverse event and to assess whether it is within the classification criteria as a serious adverse event, meaning that it requires immediate notification. The follow-up of the adverse event, even after the date of interruption of the study, will be necessary in case of persistence of the event or its sequelae. Such follow-up is necessary until the adverse event or its sequelae disappear or stabilizes to an acceptable level in the Investigator's assessment.

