#### 7.5.2. Adverse Events

Analysis of Adverse Events will be performed based on the safety population. All Adverse events will be coded using MedDRA ver. 24.1 Sept 2021

Statistical summaries will be performed on general incidence rate of treatment emergent adverse event (TEAEs) including number of events and number of participants with the events. In summarizing the number of participants with adverse events, if a participant has more than one event within the SOC (or PT) they will only be counted once in that row.

The terms Treatment Emergent Adverse Events (TEAEs) and Adverse Events (AEs) are used interchangeably below and unless otherwise specified refer to TEAEs.

Adverse Events will be summarized in the following Tables:

- Overall one page summary of TEAEs.
- Summary of TEAE's by SOC & PT sorted by total number of participants with the TEAE within a SOC and within SOC by total number of participants within a PT. This sort order will also be used in other Tables by SOC and PT indicated below.
- Summary of Severe TEAE's by SOC & PT.

- Summary of TEAE's by SOC, PT and Maximum Severity within SOC or PT. The order for displaying severity will be: Mild, Moderate, Severe.

- Summary of TEAE's Related to Study Drug by SOC PT. For this Table any AE's classified as Certain, Probable/Likely, Possible will be included.
- Summary of TEAE's by SOC, PT and Maximum Relationship to Study Drug within SOC or PT. The order for displaying Relationship to Study Drug will be: Conditional/Unclassified, Unlikely, Possible, Probable/Likely, Certain,.

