#### 7.5.3. Laboratory Test Results

All Hematology and Chemistry laboratory data will be summarized by change and % change from Baseline to each post baseline scheduled visit. For Urinalysis change and % change will only be done for pH.

Analysis of hematology and chemistry abnormalities will include a summary of abnormalities between baseline and worst post baseline visits based on criteria indicated on eCRF (Abnormal CS, Abnormal NCS, Normal, Not Done).

In addition a shift Table will display changes in status from baseline to worst post-treatment value will be summarized. The order of determining worst will be abnormal clinically significant > abnormal not clinically significant > not done.

A shift Table will summarize Serology Tests between Non-Reactive and Reactive.

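### SAP 4.2.2 defines treatment-emergent events by start date alone, so a run-in adverse event that keeps its date and worsens after the first infusion is missing from every AE table

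*SAP*

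**What the plan says.** **Definition.** SAP 4.2.2: "Treatment Emergent Adverse Events (TEAEs) are all Adverse Events that started on or after the first administration of study drug". The rule is a start date and nothing else.

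**Tables.** SAP 7.5.2: "The terms Treatment Emergent Adverse Events (TEAEs) and Adverse Events (AEs) are used interchangeably below and unless otherwise specified refer to TEAEs". Six outputs follow: an overall summary, TEAEs by SOC and PT, severe TEAEs, maximum severity, related TEAEs, and maximum relationship. The severity table, for example, is a "Summary of TEAE's by SOC, PT and Maximum Severity within SOC or PT". No table of all adverse events or of pre-treatment events is planned.

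**Collection.** Protocol 8.5: "all adverse events will be monitored and reported in the clinical form of the study from the signature of the Informed Consent". The schedule of activities has adverse-event evaluation at V-3, V-2 and V-1, all before the first infusion at V0.

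**Recording rules.** The protocol handles three kinds of finding differently.
- Physical examination (9.1): a significant finding before product goes to the clinical evaluation or history. After product, if there is "relative worsening, worsening of conditions or appearance of changes (abnormalities) during regular visits, these should be recorded as adverse events".
- ECG (7.2.4): "clinically significant abnormalities found after product administration (compared to visit V-3) should be reported and evaluated by the Investigator physician as an adverse event".
- Laboratory (9.1): abnormalities judged clinically significant and "present in the period in which the participant does not use the medicine/ investigational product should also be recorded as adverse events".

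**The concern.** The laboratory rule makes an off-product abnormality an adverse event in its own right. If it is found in the run-in, its start date precedes V0. The same is true of any clinical event noted between consent and V0, such as a fall or mild low mood. Under SAP 4.2.2 a record with that start date cannot become treatment-emergent, however intense or serious it later becomes.

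The protocol's own approach to physical findings is that worsening after product counts as an adverse event. The SAP definition does not carry this over to conditions that are already adverse-event records. Safety is a stated objective, judged by type, frequency and intensity of events, and protocol 8.5 intends the results to be shown as proportions by dose. An omission from the TEAE tables is therefore an omission from the comparison between arms that the trial sets out to make.

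**Working it through.** The plan states no figure on this point, so the check sets the provisions side by side. Arithmetic enters only in steps 5 and 6.

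1. **Can an adverse-event record predate V0?** Yes. Collection starts at consent (protocol 8.5), evaluation is scheduled at all three run-in visits, and off-product laboratory abnormalities of clinical significance are recorded as events (protocol 9.1).

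2. **Is the date firm?** Yes. SAP 7.2.1 says the eCRF did not accept partial adverse-event dates and that none will be imputed. No imputation rule can move such a record past V0.

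3. **Does any rule create a new record when the event worsens?**

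| Type of pre-dose finding | Instruction on change after dosing | Enters the TEAE tables? |
|---|---|---|
| Physical-examination finding held in history | Record worsening as an AE (protocol 9.1) | Yes, with a post-V0 start |
| ECG abnormality | Record a significant post-dose abnormality compared with V-3 (protocol 7.2.4) | Yes, with a post-V0 start |
| Laboratory abnormality recorded as an AE in the run-in | None found in either document | Only if the site opens a new record |
| Clinical AE recorded in the run-in | None found in either document | Only if the site opens a new record |

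4. **Do other outputs recover the event?** In part.
- SAP 7.1 puts all eCRF data in listings, but a listing gives no incidence by arm.
- SAP 7.5.3 summarises haematology and chemistry by change and percentage change at each scheduled visit, so a worse laboratory value contributes there. Those summaries carry no severity, seriousness or causality.
- The "shift Table will display changes in status from baseline to worst post-treatment value" works in status categories. A value already abnormal and clinically significant at baseline, and worse later, remains in the same category and shows no shift.

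5. **How long is the period in which such records can arise?** Protocol 4.4 gives up to 90 days before treatment and 330 after, and 90 + 330 = 420 days agrees with its stated total. The visit windows allow 37 + 37 + 30 = 104 days. This is the length of the collection period, not a count of affected events.

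6. **What does one omitted participant do to a row?** With planned arm sizes of 7, 14 and 14, all treated:
- Placebo: 1/7 = 14.3 percentage points.
- Each active arm: 1/14 = 7.1 points.
- Pooled active column (14 + 14 = 28): 1/28 = 3.6 points.

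These are upper limits per participant. SAP 7.5.2 counts a participant once per SOC or PT row, so nothing changes in an incidence row where that participant already has another TEAE.

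**The case against.** The strongest reply is that the loss is conditional. Protocol 9.1 defines an adverse event broadly, and a deterioration after infusion fits that definition. A site could enter it as a new event dated after V0, and it would then be tabulated. This stands, and it limits the claim to records that keep their original date. It does not remove the problem: neither document tells the site to open a new record for these two kinds of event, so capture would depend on individual practice.

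The pool of such events is also limited, and these points stand:
- Table 03 of protocol 7.2.3 and the schedule place the run-in laboratory panel at V-3 only. Abnormalities first found at V3, V7 or V11 start after V0 and are TEAEs.
- Active infection and decompensated psychiatric disease are exclusions re-checked at V0, so they are poor examples of events open at that visit.
- Signs of Huntington's disease that predate consent belong to the medical history.

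A reader might draw three stronger conclusions that the documents do not support:
- **That 21–24% of events are lost.** The figures 90/420 = 21% and 104/(104 + 335) = 24% are shares of collection time. They become shares of event onsets only if the onset rate is constant, which is doubtful when all nine infusions fall after V0. Events that start before V0 and do not worsen are also correctly not treatment-emergent.
- **That the worsening of arthritis mentioned in protocol 9.5 is an instance.** It concerns people with a history of arthritis. That is medical history rather than a run-in event, and a physical finding that worsens is covered by protocol 9.1.
- **That toxicity by arm is shown to be understated.** The definition permits understatement. Nothing in the documents shows that it occurred or in which arm. The 24-hour reporting of serious events in protocol 9.1.1 is unaffected.

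**Conclusion.** The point holds in a limited form. A run-in adverse event that is open at V0, keeps its original start date and later increases in intensity or becomes serious is excluded by definition from all six tables in SAP 7.5.2. It remains in the listings and, if it is a laboratory event, in the change-from-baseline summaries.

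The conclusion rests on two conditions: that such events exist, and that the site did not enter the worsening as a new event. The documents settle neither, so the number affected is unknown. The size per participant, up to 14 points on placebo and 7 on either active dose, assumes that all randomised participants are treated and that the participant has no other TEAE in the row. The correction should be made because arms this small make each omission visible and the remedy is cheap. It is not evidence that the safety results are wrong.

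**What to change.** 1. In SAP 4.2.2, define a TEAE as an adverse event that begins at or after the first infusion, or one present before it that increases in intensity or becomes serious at or after it. Use the date of worsening as the onset date. A later judgement that an unchanged pre-dose event is related to product should not by itself make it treatment-emergent.

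2. Before database lock, review every adverse event open at V0. Use the adverse-event records and, for laboratory events, the actual values. The visit-level clinical-significance flags are not enough, because they cannot separate a stable abnormal value from a worse one.

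3. Query the site where the date of worsening is not recorded. The documents do not show whether the eCRF holds dated changes in intensity, so some queries should be expected.

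4. List separately the events open at V0 that did not worsen.

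The cost is one sentence in the SAP, a small data-management check and possibly a few queries. No new participant assessments are needed. Reported adverse-event incidence may rise slightly.

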#### 4.2.3. Laboratory Test

Laboratory tests collected in the study and recorded in the eCRF are described in protocol Section 7.2.3 and indicated below.

- Hematology: RBC, Hemoglobin, Hematocrit, MCV, MCH, MCHC, RDW, WBC, Segmented, Typical Lymphocytes, Monocytes, Eosinophils, Basophils, Platelets, MPV.
- Chemistry: PT, INR, APTT, APTT Ratio, Glycated Hemoglobin, Amylase, Uric Acid, Total Bilirubin, Direct Bilirubin, Indirect Bilirubin, Triglycerides, Total Cholesterol, HDL, VLDL, LDL, Non-HDL, CKMB, CPK, Creatinine, Alkaline Phosphatase, Gamma GT, Potassium, Sodium, AST, ALT, Urea.
- Urinalysis as indicated on the eCRF.

Sponsor: Cellavita Pesquisa Científica Ltda.

Protocol: ADORE-DH

Statistical Analysis Plan

Version: 1.0

- Other β-hCG urinary (women-only).
- Serology: HIV (1 + 2) (Anti-HIV-1.2), HTLV I and II, HBV (HbsAg and Anti-HBc), HCV (anti-HCV-Ab) and FTA-ABS (syphilis).

#### 4.2.4. ECG

ECG data will be collected and recorded on the eCRF as indicated in the protocol Section 7.2.4 ECG data includes heart rate and whether the ECG was normal, abnormal (CS) or abnormal (NCS). Individual measurements of PR, RR, QRS, QT, etc. are not collected in this study.

#### 4.2.5. Other

#### Vital Signs

Vital signs data recorded on the eCRF will include systolic and diastolic blood pressure, pulse and respiration rate, body temperature, and SpO2 measurements.

#### **Physical Examination**

Physical Examination assessments will be as indicated in Section 7.2.2.c of the protocol and summarized in a listing. A shift Table will summarize whether the measurement was normal, abnormal (CS) or abnormal (NCS) or not done.

#### 4.3. Anti-Drug-Antibody

Not applicable

#### 4.4. Pharmacokinetics Endpoints

Not applicable

#### 4.5. Pharmacodynamics and Biomarker Endpoints

Not applicable

#### 4.6. Pharmacogenomics Endpoints

Not applicable

#### 4.7. Health Outcome Endpoints

Not applicable

#### 4.8. Demographics and Disease Characteristics

Demographic and disease characteristics collected will include Age, Sex, Race, Dominant Hand, Education Level, Height, Weight, BMI, IMC Classification, Baseline primary and secondary efficacy variables as described in Sections 4.1.1 and 4.1.2

Sponsor: Cellavita Pesquisa Científica Ltda.

Protocol: ADORE-DH

#### 4.9. Prior and Concomitant Medication

Prior medications are those taken before V0 visit.

Concomitant medications are those taken starting V0 which is the day of initiation of treatment. Prior and concomitant medications are collected on the Concomitant medications eCRF. For handling of missing or partial dates see Section 7.2.1

Prior and Concomitant medications will be grouped into categories such as Neuroleptics, Antidepressents, etc. and a Table generated for these.

#### 4.10. Protocol Deviation and Treatment Compliance

Protocol deviation will be recorded by the clinical team. Any important deviations will be summarized in the clinical study report.

Study drug administration will be recorded on the eCRF with the start and stop time of the infusion, the volume infused, the Lot/Batch information and any comments if applicable.

#### 5. Statistical Hypothesis

This study is a Phase II study to determine efficacy and safety of Cellavita HD. Hypothesis tests for efficacy will be conducted as described below. No hypothesis testing will be performed on any safety data.

All hypothesis tests will be at the two-sided 5% significance level (Two-sided Type I error of 0.05)

H0: There is no difference in rate of change (slope) per year from Baseline through V11 in TMS between the two pooled active treatment groups and the placebo group

Ha: There is a difference in rate of change (slope) per year from Baseline through V11 in TMS between the two pooled active treatment groups and the placebo group

The following statistical tests will be performed:

- 1. Between the two active pooled treatment groups and placebo (primary)
  Participants receiving either 1 million or 2 million cells per kg (Treated) vs. Placebo
- Between each of the two active treatment groups individually and placebo (to determine efficacy of each treatment group compared to placebo)
   Participants receiving 1 million cells per kg (Treated) vs. Placebo
   And Participants receiving 2 million cells per kg (Treated) vs. Placebo
- 3. Between the two active treatment groups to assess similarity between the two treatment groups.

F-SA-06-01, Version 5.0/30 Dec 2021, SOPs Link: SOP-SA-06

Participants receiving 1 million vs. 2 million cells per kg.

The same tests performed for TMS will also be performed for other continuous endpoints.

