Cell and genetic therapies are considered innovative therapies for which there are no fully defined guides and guidelines in Brazil and on the world stage. However, in June 2015, the U.S. regulatory agency FDA (*Food and Drug Administration*) published a document entitled *Considerations for the Design of Early-Phase Clinical Trials of Cellular and Gene Therapy Products - Guidance for Industry* representing the FDA's current recommendations on the first clinical studies with cell and gene therapy. The present study called ADORE-DH (EVALUATION OF THE DOSE-RESPONSE OF CELLAVITA HD INVESTIGATIONAL PRODUCT AFTER INTRAVENOUS APPLICATION IN PARTICIPANTS WITH HUNTINGTON'S DISEASE) has as main objective to identify the dose of the Cellavita HD product that presents the best or most appropriate dose-response relationship, that is, that provides maximum efficacy and is considered safe. The definition of the most appropriate dose in the early stages of

the clinical study is decisive for a more optimized clinical development (FDA, 2015; FDA, 2010; Chow & Chang, 2008).

The target population of the ADORE-DH study will consist of participants of both genders, with laboratory diagnosis of Huntington's disease, with mild to moderate symptoms and that justifies the risks inherent to a new product, but at the same time, is able to provide results that can be interpreted for dose-response evaluation of the same.

The methodology to be used for the evaluation of the primary outcome (identification of the best dose) will be the score obtained in the evaluation in the motor part of the UHDRS scale (motor test), since motor degradation is considered one of the main aspects of Huntington's disease (ADF, 2010; Paulsen et al., 2014). As secondary objectives, other components of the UHDRS scale will be evaluated, as well as BMI and morphological aspects of the central nervous system by Magnetic Resonance. The safety of the investigational product will also be evaluated through the incidence and classification of adverse events presented by the participants during the study.

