Thus, with the identification of the dose of the Cellavita-HD product that presents the best response, measured from the parameters established in this protocol, the next planned studies can be initiated. The present study coded as ADORE-DH, corresponds to the second study of the development plan for the process of registration of the Cellavita-HD investigational product with the competent agencies.

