3. OBJECTIVES

3.1. Primary objective of effectiveness

The primary objective of this clinical trial is to identify the dose of Cellavita-HD product that has the best clinical response.

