8.6. Study hypotheses

8.6.1. Primary Hypothesis

Identify the dose of the Cellavita-HD investigational product that presents the best response.

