### 2. Study Objective (s)

The primary objective of this clinical trial is to identify the dose of Cellavita-HD product that has the best clinical response (Total Motor Scale from UHDRS).

The secondary efficacy objectives of the study are:

- Clinical neurological evaluation throughout the study (Other domains from UHDRS and HAM-D)
- Overall assessment of Huntington's disease severity (CIBIS scale)
- BMI assessment
- Assess the incidence of suicide attempts during treatment
- Neurological evaluation by imaging

The safety objective of the study is to evaluate the incidence and classification of adverse events occurring between treatments regarding type, frequency and intensity as well as abnormalities in safety data such as ECGs, Vital Signs, Chemistry & Hematology laboratory assessments, etc.

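### A 5% low-versus-high comparison with no margin cannot show that the doses are similar, and the SAP does not say how its dose-level results answer the best-dose objective

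*SAP*

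**What the plan says.** Protocol 3.1 states: "The primary objective of this clinical trial is to identify the dose of Cellavita-HD product that has the best clinical response". Protocol 8.6.1 gives the primary hypothesis as: "Identify the dose of the Cellavita-HD investigational product that presents the best response". SAP section 2 keeps this aim and ties it to the motor score: "identify the dose of Cellavita-HD product that has the best clinical response (Total Motor Scale from UHDRS". Protocol section 2 describes the wanted dose as one "that provides maximum efficacy and is considered safe", and says the next planned studies can start "with the identification of the dose of the Cellavita-HD product that presents the best response".

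SAP section 5 writes one null hypothesis: the annual TMS slope from baseline to V11 does not differ between the pooled active groups and placebo. SAP 7.4.1 repeats it. Section 5 then lists three sets of tests:

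1. "Between the two active pooled treatment groups and placebo (primary".
2. Each dose separately against placebo.
3. "Between the two active treatment groups to assess similarity between the two treatment groups".

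One level covers them all: "All hypothesis tests will be at the two-sided 5% significance level (Two-sided Type I error of 0.05". The same tests are to be run on the other continuous endpoints.

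Dose-level output is planned. SAP 7.1 gives low, high, combined and placebo columns. SAP 7.4.1 gives least-squares means per group and 95% confidence intervals for the comparisons at post-baseline visits.

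**The concern.** There are two gaps and one minor omission.

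**Similarity.** A two-sided 5% test asks whether a difference has been shown. If it is not significant, the data are compatible with no difference and also with every other value inside the confidence interval. To conclude similarity, that interval must be compared with a margin, and neither document has one. A non-significant result could therefore be read as showing that the doses are alike when the trial was simply too small to separate them.

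**Best dose.** The pooled contrast averages the two doses, so it carries no information on which is better. It can succeed or fail and leave the primary objective open. The dose-level estimates could fill the gap, but no section of either document says which estimate decides, or how. Since later studies depend on the answer, a criterion left unwritten could be chosen after the results are seen.

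**Multiplicity (minor).** Protocol 8.7.1.1.1 and 8.7.1.1.2 promise adjustment for multiple comparisons. The SAP, which in 7.6 says that it supersedes the protocol's analysis, states none for the dose-level tests and does not call their p-values nominal.

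**Working it through.** **Inputs from the documents.** 35 participants at 2:2:1 (Protocol 4.3, SAP section 3): 35 × 2/5 = 14 low, 14 high, and 35 × 1/5 = 7 placebo, which agrees with the stated split. Two-sided level 5% (SAP section 5). Protocol 8.1 bases the 35 on non-statistical grounds, so there is no power figure to reproduce.

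**Assumptions.** Effects are in SD units of the endpoint, because no SD, effect or margin is given. A three-arm comparison with common SD, no dropout and 35 − 3 = 32 degrees of freedom stands in for the MMRM slope contrasts.

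**Precision of low versus high.**
- SE = √(1/14 + 1/14) = 0.378.
- 95% half-width = 2.037 × 0.378 = 0.770.
- 90% half-width = 1.694 × 0.378 = 0.640.

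**Chance of a non-significant result when the doses truly differ** (noncentral t, noncentrality d/0.378):

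| True difference d | Noncentrality | Non-significant |
|---|---|---|
| 0.5 SD | 1.32 | 75% |
| 0.76 SD | 2.02 | 50% |
| 1 SD | 2.65 | 27% |

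With an assumed dropout to 12/12/6, the figures are 78% at 0.5 SD and 34% at 1 SD.

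**Chance that a margin-based similarity claim succeeds when the doses are identical** (interval wholly inside the margin, integrated over the variance estimate):

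| Margin | 95% CI | 90% CI |
|---|---|---|
| ±1 SD | 46% | 65% |
| ±0.8 SD | 12% | 33% |
| ±0.5 SD | under 0.1% | 0.2% |

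**What the pooled test says about ranking.** SE = √(1/28 + 1/7) = 0.423.
- If both doses work by 1 SD, it is significant in 63% of trials and silent on which dose is better.
- If only one works by 1 SD, the pooled effect is 0.5 SD and the test is significant in 21%. That dose against placebo (SE √(1/14 + 1/7) = 0.463) is significant in 55%.

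**What the dose estimates can say.** The truly better dose has the better estimate with probability Φ(d/0.378): Φ(1.32) = 91% at 0.5 SD and Φ(2.65) = over 99% at 1 SD. If neither dose works, the better-looking dose still beats placebo numerically with probability 1 − (1/4 + arcsin(2/3)/2π) = 63%. The choice therefore needs each dose's interval against placebo beside it.

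**Multiplicity.** With no true effect, simulation of 4,000,000 trials gives at least one dose differing significantly from placebo, in either direction, in 8.4%. By symmetry half of these are in the favourable direction, so a dose is called better than placebo in about 4.2%. The pooled test stays at 5%.

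**The case against.** The best reply is that most of what is needed is already planned. SAP section 5 lists each dose against placebo and low against high. SAP 7.4.1 promises 95% intervals for the comparisons, and the natural reading is that these include the ones listed in section 5. V11 is a post-baseline visit. Picking the better estimate would usually be right at moderate true differences. One test is clearly marked primary and is valid. The trial is a small phase II study whose size is openly not statistical, and the figures above rest on assumed effects and a simplified model that SAP 7.4.1 says may change.

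Much of this stands, and it limits the point. A reader might infer that the plan gives no dose-level information; it does. A reader might infer that the primary test has an inflated error rate; it does not. A reader might take 8.4% as the chance of wrongly declaring a dose effective, but that figure counts harm as well as benefit. Nor does any section say that non-significance will be reported as similarity. Because no null is written for that comparison, calling it a difference test is an inference, though every hypothesis that is written has that form.

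What the reply does not meet is narrower. An interval without a margin gives no basis for a similarity conclusion, and a list of estimates is not a stated answer to the objective.

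**Conclusion.** The concern holds in this limited form and should be fixed. As worded, the low-versus-high comparison is given a purpose that it cannot serve. At 14 per dose it would miss a true 0.5 SD difference in 75% of trials and a 1 SD difference in 27%. These sizes rest on assumed effects and the three-arm approximation; the logical point does not depend on them.

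The primary objective and the primary test ask different questions, and the link between the planned dose-level results and the objective is unwritten. This does not make the pooled test wrong or mean it must be replaced: it answers whether the product works at all. The multiplicity gap is minor and affects dose-level claims only.

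**What to change.** All changes are in SAP section 5.

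1. Replace the similarity purpose of the third comparison with estimating the low-minus-high difference in TMS slope to V11 with its 95% confidence interval. Allow a similarity claim only if the interval (95%, or 90% for a two one-sided test at 5%) lies inside a margin stated before unblinding.
2. State that the pooled test addresses whether the product works at all. State that, on efficacy, the best-dose objective is answered by the dose with the more favourable estimated TMS slope; a smaller annual rise is better, since higher TMS is worse. Report it with the low-minus-high interval and each dose's interval against placebo, as an estimate and not as an error-controlled conclusion. Whether and how safety enters the choice is for the sponsor to state.
3. Label dose-level and other-endpoint p-values as nominal.

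If the data are already unblinded, label the criterion and any margin as post hoc.

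The cost is wording only, with no extra participants or assessments. The downside is that similarity could rarely be claimed: even with identical doses, the 95% interval falls inside ±1 SD in 46% of trials and inside ±0.5 SD in under 0.1%. Dose-level p-values would also carry no confirmatory weight.
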